#### 8.5.1.1 Pharmacokinetic Blood collection and handling

Blood samples will be taken by either direct venipuncture or an indwelling cannula inserted in a forearm vein. At specified time points described in Table 8-6, 1-1.2 mL blood draws will be collected into tubes containing an anticoagulant and gently inverted several times to thoroughly mix the anticoagulant. 1 mL of blood will be transferred into a vial for radioactivity measurement in the well/gamma-counter.

[figure not shown]
All data including but not limited to actual date and time of blood sampling, date and time of measurement by well/gamma-counter, exact volume of sample measured (including any dilutions if applicable) and activity counted by well/gamma counter must be recorded in the appropriate blood collection eCRF page.

[figure not shown]

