**Table 8-6 Pharmacokinetic blood collection log (PK patient subset only)**

Dose Reference ID	Treatment Period or Cycle	Day	Scheduled Time (post-dose/injection)	PK Sample No
1	1	1	Pre-dose (before injection)	101

Dose Reference ID	Treatment Period or Cycle	Day	Scheduled Time (post-dose/injection)	PK Sample No
1	1	1	0-5 min	102
1	1	1	15 min ( $\pm$ 5 min)	103
1	1	1	30 min ( $\pm$ 5 min)	104
1	1	1	1 h ( $\pm$ 15 min)	105
1	1	1	2 h ( $\pm$ 30 min)	106
1	1	1	3-4 h	107
1	1	1	5 h ( $\pm$ 30 min)*	108

\* This sample is optional but clinical logistics permitting effort should be taken to collect this sample

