# 2.9 Pharmacokinetic endpoints

All PK analyses will be carried out on the PAS.

The [F]CTT1057 pharmacokinetic analysis will be performed based on decay-corrected blood radioactivity concentration data obtained by measuring the blood samples drawn at pre-defined time points (Table 8-6 of the protocol) using a calibrated gamma-counting device. Blood mass concentration data were also planned to be summarized per protocol, however the conversion

Novartis	Confidential	Page 33 of 43
SAP Amendment 2		Study No. CAAA405A12302

of radioactivity concentration to mass concentration will not be possible due to missing information of mass concentration of the drug product during the manufacturing process.

Radioactivity concentration in blood will be calculated using the following formula:

$$RDCNNDB = (ACTMENDC / SAMPVOL) / DURSFLT1$$

where, RDCNNDB is radioactivity concentration in blood (not decay corrected), ACTMENDC is radioactivity measured (not decay corrected), SAMPVOL is volume of the sample measured, and DURSFLT1 is gamma counter calibration factor.

Decay correction of the radioactivity concentration in blood will be performed using the following formula:

$$RDCNDCB = RDCNNDB \times e^{-\lambda \cdot (RDACTDAT \& TIM - ECSTDTC)}$$

where, RDCNDCB is radioactivity concentration in blood (decay corrected),  $\lambda$  is decay constant, RDACTDAT&TIM is radioactivity measurement date and time, and ECSTDTC is dose administered date and time.

Decay constant ( $\lambda$ ) is calculated using the following formula:

$$\lambda = \frac{ln^2}{t_{1/2}}$$

where, t1/2 is half-life of 18-F which is 109.7 min.

Blood radioactivity concentration data will be listed by participant and visit/sampling time point. Pharmacokinetic parameters will be listed by participant. Descriptive summary statistics will be provided by visit/sampling time point. Summary statistics will include mean (arithmetic and geometric), standard deviation (SD), coefficient of variation (CV) (arithmetic and geometric), median, minimum, and maximum. An exception to this is Tmax, where only median, minimum, and maximum will be presented.

The following pharmacokinetic parameters will be determined using the actual recorded sampling times and non-compartmental method(s) with Phoenix WinNonlin® (Version 8 or higher): Cmax, Tmax, AUClast, AUCinf, T1/2, Vz and CL (Table 2-4).

 Table 2-4
 Non-compartmental pharmacokinetic parameters

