# $RDCNNDU = \left(\frac{ACTMENDC}{SAMPVOL}\right) / DURSFLT1$

where, RDCNNDU is radioactivity concentration in urine (not decay corrected), ACTMENDC is radioactivity measured (not decay corrected), SAMPVOL is volume of the sample measured, and DURSFLT1 is gamma counter calibration factor.

Decay correction of the radioactivity concentration in urine will be performed using the following formula:

$$RDCNDCU = RDCNNDB \times e^{-\lambda \cdot (RDACTDAT \&TIM - ECSTDTC)}$$

where, RDCNDCU is radioactivity concentration in urine (decay corrected),  $\lambda$  is decay constant, RDACTDAT&TIM is radioactivity measurement date and time, and ECSTDTC is dose administered date and time.

Decay constant ( $\lambda$ ) is calculated using the following formula:

$$\lambda = \frac{ln^2}{t_{1/2}}$$

Novartis	Confidential	Page 35 of 43
SAP Amendment 2		Study No. CAAA405A12302

where, t1/2 is half-life of 18-F which is 109.7 min.

The percentage of injected activity (%ID) will be calculated using the following formula:

 $PCTINDS = (\frac{RDCNDCU \times SAMPCOL}{ECDOSE \times 1000}) \times 100(\%)$ 

where, PCTINDS is percentage of injected activity (%ID) in urine, and ECDOSE is decaycorrected administered dose (MBq).

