# 4 Change to protocol specified analyses

Minor updates to the estimand wording were made as compared to the protocol for clarification.

Blood mass concentration data were planned to be summarized per protocol as part of the PK analysis, however the conversion of radioactivity concentration to mass concentration will not be possible due to missing information of mass concentration of the drug product during the manufacturing process. Section 2.9 of the SAP clarifies the analyses that will be summarized.

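### The decay-correction formulas for blood and urine in SAP 2.9 carry the wrong sign, so they apply physical decay a second time instead of undoing it

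*SAP*

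**What the plan says.** SAP 2.9 bases the PK analysis on radioactivity counted in blood and urine and corrected for the decay of 18F. The steps are:

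- The uncorrected concentration is measured activity divided by sample volume and by the counter's calibration factor. The SAP is explicit that this input is raw: "RDCNNDB is radioactivity concentration in blood (not decay corrected), ACTMENDC is radioactivity measured (not decay corrected".
- Blood is corrected by "RDCNDCB = RDCNNDB \times e^{-\lambda \cdot (RDACTDAT \& TIM - ECSTDTC". RDACTDAT&TIM is the counting time and ECSTDTC the dosing time. Lambda comes from a half-life of 109.7 min.
- Urine is corrected by "RDCNDCU = RDCNNDB \times e^{-\lambda \cdot (RDACTDAT \&TIM - ECSTDTC". The exponent is the same, and the variable on the right is the blood one, although RDCNNDU is defined just above.
- Urinary %ID has the corrected urine concentration in its numerator. In its denominator, "ECDOSE is decaycorrected administered dose (MBq".

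The corrected blood data feed Cmax, Tmax, AUClast, AUCinf, T1/2, Vz and CL. Protocol 12.5.3 says only that the data are decay-corrected and gives no formula. SAP 4 explains why the conversion to mass units was dropped and then refers the reader back: "Section 2.9 of the SAP clarifies the analyses that will be summarized".

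For blood, Protocol 8.5.1.1 requires the "date and time of measurement by well/gamma-counter" to be recorded, but does not say when counting must take place.

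**The concern.** Activity counted after dosing has already fallen through physical decay. Correcting it back to dosing time must raise it. The printed factor is below 1 for every post-dose sample, so it lowers the value again.

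These are the only working formulas in either document, and they are written in dataset variable names that a programmer could code directly. Because the mass conversion has been dropped, decay-corrected radioactivity is the sole basis for the PK objective. Programmed as printed, the formulas would make the tracer appear to leave the blood much faster than it does and would understate urinary excretion. The size of the error would also depend on when the site happened to count its samples.

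**Working it through.** Neither document gives a PK result, so there is no stated figure to reproduce. The check follows from the SAP's own definitions.

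**Inputs.** From SAP 2.9: half-life 109.7 min, so lambda = ln 2 / 109.7 = 0.006319 per min (the extracted text shows ln², read here as ln 2). From Protocol Table 8-6: samples at 0–5, 15, 30, 60 and 120 min, 3–4 h and 5 h, taken as 2.5, 15, 30, 60, 120, 210 and 300 min. The 5 h sample is optional: "This sample is optional but clinical logistics permitting effort should be taken to collect this sample". Assumed, because the documents do not give them: the blood half-life and the counting times.

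**Step 1, direction.** With t = counting time minus dosing time, measured = true × exp(−lambda × t). Hence true = measured × exp(+lambda × t). The printed formula gives measured × exp(−lambda × t) = true × exp(−2 × lambda × t).

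**Step 2, size per sample.**

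| t from dosing to counting | Correct multiplier | Printed multiplier | Too low by |
|---|---|---|---|
| 60 min | 1.46 | 0.685 | 2.13-fold |
| 109.7 min | 2.00 | 0.500 | 4.00-fold |
| 120 min | 2.13 | 0.468 | 4.56-fold |
| 210 min | 3.77 | 0.265 | 14.2-fold |
| 300 min | 6.66 | 0.150 | 44.3-fold |

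**Step 3, PK parameters, samples counted as drawn.** Assume a mono-exponential curve with true T1/2 = 180 min, so k = ln 2 / 180 = 0.003851 per min. The error adds 2 × lambda = 0.012637 to the slope, which becomes 0.016488.

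- T1/2 = ln 2 / 0.016488 = 42.0 min.
- AUCinf ratio = 0.003851 / 0.016488 = 0.234, so CL is 1 / 0.234 = 4.28 times too high.
- AUClast ratio to 300 min = 0.234 × (1 − exp(−4.946)) / (1 − exp(−1.155)) = 0.339.
- Cmax ratio at 2.5 min = exp(−2 × lambda × 2.5) = 0.969.
- Vz = CL / slope: 4.28 × 0.234 = 1.00, unchanged.

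True half-lives of 60, 120 and 360 min would be reported as 28.7, 37.6 and 47.6 min, with CL 2.09, 3.19 and 7.56 times too high. With prompt counting and a declining curve, no reported T1/2 can exceed ln 2 / (2 × lambda) = 54.85 min.

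**Step 4, other counting patterns (true T1/2 180 min).**

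| Pattern | T1/2 reported | Cmax ratio | CL ratio | Vz ratio |
|---|---|---|---|---|
| Counted as drawn | 42.0 min | 0.969 | 4.28 | 1.00 |
| Each counted 30 min after draw | 42.0 min | 0.663 | 6.26 | 1.46 |
| All counted together at 6 h | 180 min | 0.0106 | 94.6 | 94.6 |
| Bi-exponential (half-lives 10 and 180 min, weights 70/30), counted as drawn | 42.0 min | 0.969 | 3.27 | 0.76 |

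Tmax did not change in any of these. With the sign corrected, every parameter returns to its true value under every counting pattern tried.

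**Step 5, urine.** %ID is proportional to the corrected urine concentration. If the administered dose is referenced to dosing time and the urine is counted at an assumed 1, 2 or 4 h, the reported %ID is exp(−2 × lambda × t) = 0.469, 0.219 or 0.048 of the true value.

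**Step 6, variable name.** "RDCNDCU = RDCNNDB" uses the blood variable. The expressions for RDCNNDB and RDCNNDU have the same right-hand side, so this is a labelling slip that changes the result only if blood values are actually read in.

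**The case against.** Four points can be made on the other side.

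1. The equations were read from a PDF, and the same block shows a misreading (ln² for ln 2). A minus sign is one character. However, it appears in both formulas with the two times in the same order. The urine formula may have been copied from the blood one, so the two are not fully independent evidence. A misread remains unlikely, and looking at the SAP source would settle it.
2. The intent is clear, since the outputs are labelled as decay corrected and a careful programmer may have used the right sign. The documents do not show the program. This makes the consequences conditional; it does not make the specification right.
3. The stakes are limited: a descriptive analysis in about 10 participants, with no test or success criterion attached, and raw counts retained so that results could be recalculated. All of that stands.
4. The size depends on assumed half-lives and counting times. Only the factor exp(−2 × lambda × t) follows from the documents. The 95-fold case is one possible counting pattern, not an expected effect. Recording of counting times is also stated explicitly only for blood in the available text. For urine, Protocol 8.5.1 mentions recorded counts, although the SAP urine formula itself takes a counting time as input.

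**Conclusion.** The error is real. From the SAP's own definitions, both formulas apply decay twice, and no other section of either document gives the right version. The factor exp(2 × lambda × t) per sample is certain once the printed sign is confirmed. The effect on each parameter depends on counting practice:

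- Cmax is only about 3% low if the first sample is counted at once, but much lower with delay.
- AUClast and AUCinf are too low and CL too high under every pattern examined.
- T1/2 is too short unless the samples that determine the terminal slope share one counting time.
- Vz is unaffected only for a mono-exponential curve with prompt counting.
- Urinary %ID is too low whenever urine values are used.

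The co-primary analyses are untouched. The formulas should nevertheless be corrected before any PK output is relied on, because the specification is wrong as written and the possible error is several-fold.

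**What to change.** In SAP 2.9, replace the two formulas with:

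- Blood: RDCNDCB = RDCNNDB × exp(+lambda × (RDACTDAT&TIM − ECSTDTC))
- Urine: RDCNDCU = RDCNNDU × exp(+lambda × (RDACTDAT&TIM − ECSTDTC))

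Confirm the printed sign against the SAP source file. Then run one test record through the PK program: a sample counted 109.7 min after dosing must be multiplied by 2.00, whereas the printed formula gives 0.50. While there, state the time to which ECDOSE is decay-corrected, since %ID is valid only if numerator and denominator share a reference time.

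The cost is two signs, one variable name, one clarifying phrase and a short programming check. Blood needs no new data, because counts, volumes and counting times already go into the eCRF. For urine, confirm that the counting time is captured there too.

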# $RDCNNDU = \left(\frac{ACTMENDC}{SAMPVOL}\right) / DURSFLT1$

where, RDCNNDU is radioactivity concentration in urine (not decay corrected), ACTMENDC is radioactivity measured (not decay corrected), SAMPVOL is volume of the sample measured, and DURSFLT1 is gamma counter calibration factor.

Decay correction of the radioactivity concentration in urine will be performed using the following formula:

$$RDCNDCU = RDCNNDB \times e^{-\lambda \cdot (RDACTDAT \&TIM - ECSTDTC)}$$

where, RDCNDCU is radioactivity concentration in urine (decay corrected),  $\lambda$  is decay constant, RDACTDAT&TIM is radioactivity measurement date and time, and ECSTDTC is dose administered date and time.

Decay constant ( $\lambda$ ) is calculated using the following formula:

$$\lambda = \frac{ln^2}{t_{1/2}}$$

Novartis	Confidential	Page 35 of 43
SAP Amendment 2		Study No. CAAA405A12302

where, t1/2 is half-life of 18-F which is 109.7 min.

The percentage of injected activity (%ID) will be calculated using the following formula:

 $PCTINDS = (\frac{RDCNDCU \times SAMPCOL}{ECDOSE \times 1000}) \times 100(\%)$ 

where, PCTINDS is percentage of injected activity (%ID) in urine, and ECDOSE is decaycorrected administered dose (MBq).

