AUC%Extrap 	Area under the plasma concentration-time curve extrapolated from the time t to infinity as a percentage of total AUC (%)
AUClast	The AUC from time zero to the last measurable concentration sampling time (tlast) (mass x time x volume  )
AUCinf	The AUC from time zero to infinity (mass x time x volume  )
Clast 	Last measurable concentration (mass x volume  )
Cmax	The maximum (peak) observed plasma, blood serum, or other body fluid drug concentration

	after single dose administration (mass x volume  )
Tmax	The time to reach maximum (peak) plasma, blood, serum, or other body fluid drug concentration after single dose administration (time)
T 1/2	The elimination half-life associated with the terminal slope ( $\lambda z$ ) of a semi logarithmic concentration-time curve (time)
Tlast 	Last measurable concentration sampling (time)
Rsqadj 	Square of the correlation coefficient associated with lambda_z
CL	The total body clearance (CL) of drug from plasma, blood serum, or other body fluid drug concentration (volume x time  )
Vz	The apparent volume of distribution during terminal phase (associated with $\lambda z$ ) (volume)

 AUC%Extrap and Rsqadj will be used in the interpretation of the primary PK parameters and therefore will be included in the listings only.

 Clast and Tlast will only be listed but not summarized

The elimination of the compound in urine will be evaluated based on decay-corrected urine radioactivity concentration data obtained by measuring the urine samples drawn at pre-defined time points (Table 8-7 of the protocol) using a calibrated gamma-counting device. Urine elimination data will be expressed as the percentage of injected activity (%ID) in each specified time interval and also as cumulative %ID excreted up to the end of each time interval. Urine elimination data will be listed by participants. Descriptive summary statistics will include mean (arithmetic and geometric), SD, CV (arithmetic and geometric), median, minimum, and maximum.

Radioactivity concentration in urine will be calculated using the following formula:

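### SAP 2.9 prints the blood variable RDCNNDB, not the urine variable RDCNNDU, as the input to the urine decay-correction formula that feeds urinary %ID

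*SAP*

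**What the plan says.** SAP Section 2.9 keeps separate variables for the two matrices. On the blood side, "RDCNNDB is radioactivity concentration in blood (not decay corrected"; its decay-corrected counterpart is built from "RDCNDCB = RDCNNDB" and the decay factor. On the urine side, "RDCNNDU is radioactivity concentration in urine (not decay corrected", and the target of the next formula is described in the same terms: "RDCNDCU is radioactivity concentration in urine (decay corrected". That urine formula, however, reads "RDCNDCU = RDCNNDB" times the decay factor, which is the same right-hand side as the blood formula.

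The prose states the intent. The urine analysis is to use "decay-corrected urine radioactivity concentration data obtained by measuring the urine samples drawn at pre-defined" time points, and "Urine elimination data will be expressed as the percentage of injected activity (%ID) in each specified time interval", and also cumulatively. The %ID formula has "RDCNDCU \times SAMPCOL" in its numerator and the administered dose in MBq times 1000 in its denominator.

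SAP Section 4, which lists changes from the protocol, mentions only the estimand wording and the dropped conversion to mass concentration. Protocol Section 12.5.3 does not resolve the matter: its own urine paragraph attributes the urine data to blood samples. The SAP changed that word in the prose, but the formula still carries the blood term.

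**The concern.** RDCNNDU is computed and then goes nowhere, while the variable that does feed the urine chain belongs to the other matrix. Followed to the letter, no quantity labelled as a urine concentration reaches the %ID calculation. Quantification of urinary excretion is named within the secondary PK endpoint (protocol Table 2-1, SAP Table 1-1), so this is the specified derivation of a listed output. SAP Section 1 also presents the document as the record of analysis decisions taken before database lock. If the program is right only because someone silently departed from the printed formula, that departure is not on record.

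**Working it through.** The documents state no %ID value, so there is no figure to reproduce. The check is to substitute the printed formulas into one another.

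**Inputs (SAP 2.9)**
- Uncorrected concentration, with the same expression for RDCNNDB and RDCNNDU: (ACTMENDC / SAMPVOL) / DURSFLT1.
- Decay factor as printed: D = exp(−λΔt), where Δt is measurement time minus dose time. With a half-life of 109.7 min, λ = ln 2 / 109.7 = 0.00632 per min. The exponent-like 2 printed on ln is taken to be a PDF reading artefact.
- %ID = 100 × RDCNDCU × SAMPCOL / (ECDOSE × 1000).

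**Assumptions (not in the documents)**
- SAMPCOL is not defined in the SAP; it is read here as the collected urine volume in mL.
- R = RDCNNDU / RDCNNDB, the urine-to-blood concentration ratio, is set to 2, 10 and 50.
- For the illustration: 370 MBq injected (the nominal activity), 300 mL of urine, blood at 5 kBq/mL, counted at Δt = 120 min.

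**Step 1: substitute**
- As printed: %ID = 100 × RDCNNDB × D × SAMPCOL / (ECDOSE × 1000).
- With the urine input: %ID = 100 × RDCNNDU × D × SAMPCOL / (ECDOSE × 1000).

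**Step 2: take the ratio.** With the same Δt in both lines, everything but the concentration cancels: printed / urine-based = RDCNNDB / RDCNNDU = 1/R.

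**Step 3: put numbers in.** At 120 min, D = exp(−0.00632 × 120) = 0.468. As printed: 100 × 5 × 0.468 × 300 / (370 × 1000) = 0.19 %ID.

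| Assumed R | Printed, blood value used | Urine input, printed exponent kept | Printed / urine-based |
|---|---|---|---|
| 2 | 0.19 | 0.38 | 50% |
| 10 | 0.19 | 1.90 | 10% |
| 50 | 0.19 | 9.50 | 2% |

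If R differs between collection intervals, no single factor rescales cumulative %ID; it has to be recomputed from the urine counts.

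**Step 4: what a program would do with the printed line**
- It fetches RDCNNDB from blood records: the error is 1/R, as in the table.
- It looks for RDCNNDB on urine records where no such variable exists: the derivation finds no input.
- It evaluates the shared expression on urine records under the blood label: the concentration is the urine one, because the two definitions are algebraically identical.

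**Step 5: what the symbol change does not repair.** D is below 1 for any count after dosing, whereas bringing a later count back to dose time requires exp(+λΔt). The printed sign understates the dose-time value by exp(2λΔt): 2.1 at 60 min, 4.6 at 120 min and 20.8 at 240 min. The urine-input column above is therefore not a correct %ID either; it isolates the effect of the input symbol.

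**The case against.** The best reply is that this is a one-letter carry-over from the blood formula and that the intended meaning is plain. The lead-in to the formula, the description of its output and the preceding prose all say urine. The shared right-hand side means that a program run on urine records returns the urine concentration whichever label it uses. A blood value enters only if someone joins blood time points to urine collection intervals; the SAP describes no such pairing, and protocol Section 8.5.1 has counts recorded on the respective blood or urine eCRF pages. The output is descriptive, has no hypothesis or threshold, and concerns about 10 consenting participants at one site. Raw counts are recorded, so a faulty derivation can be rerun.

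Most of this stands, and it limits the consequence. A reader might infer that urinary %ID will be blood activity times urine volume. The documents do not support that: it is one of three possible outcomes and needs a merge that the SAP does not specify. A reader might also attach a single multiple to the error. Assumed concentrations of 100 kBq/mL in urine and 5 kBq/mL in blood would give 20-fold, but that is only the ratio of two chosen numbers, and neither is in the documents.

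What does not fall away is the text. The printed formula conflicts with the SAP's own definitions and no other section corrects it. A misread letter in the PDF is possible but unlikely, since RDCNNDU is read correctly twice beside the formula.

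**Conclusion.** The input symbol in the urine decay-correction formula is wrong as printed. That conclusion rests on the SAP's definitions alone, subject to confirming the letter in the source PDF. The size of any numerical error is conditional: it arises only if blood records supply RDCNNDB, and then equals RDCNNDB/RDCNNDU, that is 50%, 10% or 2% of the urine-based value for assumed ratios of 2, 10 and 50. The absolute %ID figures also depend on reading SAMPCOL as urine volume; the ratio does not.

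Severity is moderate. A named secondary output lacks a correct printed derivation, but it is descriptive, covers about 10 participants and can be recovered from stored counts. The co-primary endpoints, the reader success rule, the sample size and the blood PK parameters do not use this input. Nor should the symbol change be taken as making %ID correct: the exponent sign is a separate fault in the same line.

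**What to change.** Check the symbol against the source PDF of SAP Section 2.9. If it reads as extracted, replace RDCNNDB with RDCNNDU on the right-hand side of the RDCNDCU formula, and confirm that the matching program line uses the urine variable from urine records. Define SAMPCOL and its unit in the same edit. Correct the exponent sign as a separate item, since %ID will not be right without it. Then calculate cumulative %ID by hand for one participant from the recorded urine counts and compare it with the program output.

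The cost is one symbol in the SAP, one program line to check and one hand calculation. No new data are needed.
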